7.11.2 Electrocardiogram

Descriptive statistics for the absolute measurements and changes from baseline for selected ECG parameters will be reported. These include the following intervals: QT, QT corrected for heart rate, the time elapsed from the onset of atrial depolarization to the onset of ventricular depolarization (PR), and time elapsed for depolarization of the ventricles (QRS).

The frequency of subjects with a maximum increase from baseline in the QTc interval will be summarized according to the following categories: > 30 ms and > 60 ms. In addition, the frequency of subjects with QTc post dose values according to the following categories: > 450 ms, > 480 ms and > 500 ms, will be summarized.

The normality or abnormality of the ECG tracing will be summarized using shift tables of numbers of subjects who have a normal/abnormal ECG tracing at each scheduled time of assessment.

A listing of all ECG parameters including the overall assessment will also be created.

7.11.3 Urine Pregnancy Test

Urine pregnancy test results will be listed.

8 CHANGES TO ANALYSES SPECIFIED IN PROTOCOL

Due to administrative reasons, the study terminated after enrollment of 4 subjects in Cohort 1S and 4 subjects in Cohort 2S. As such, only analyses specific to SAD cohorts 1S and 2S will be provided.


10 APPENDICES

10.1 Handling of Missing and Incomplete Data

Missing clinical outcome data can occur for multiple reasons, including missed subject visits and scales or measures with missing item scores. Missing and incomplete data will be identified through the data quality review plan for this study. Missing and incomplete data will be identified for investigation, and possible resolution, by Data Management prior to the study database lock or snapshot.

Unless specified otherwise, only the observed data (not imputed data) will be presented in listings.

10.1.1 Missing Medical History Related Dates

- If only day is missing, impute 1.
- If month is missing, impute January 1st.
- If year is missing, then no imputation will be done; the date will be missing.
- If the imputed start date is earlier than the birth date, then the birth date will be used.
- If the imputed end date is earlier than the start date, the start date will be used.

10.1.2 Missing Birth Dates

To impute missing birth date, the following rules will be applied:

- If day is missing, impute 15.
- If month is missing, impute June.
- If year is missing, then no imputation will be done; the date will be missing.

If the imputed date is later than any study visit date/observed adverse event start date/observed concomitant medication start date, then earliest available visit date/adverse event start date/ concomitant medication start date will be used without changing observed information.

10.1.3 Missing Date Imputation for Adverse Events and Concomitant Medications

The following conventions will be used to impute missing portions of dates for adverse events and concomitant medications. Note that the imputed values outlined here may not always provide the most conservative date.

Missing Start Dates

- If the day is unknown, then:
 - If the month and year match the first dose of investigational product start date month and year in this study, then impute the day of the first dose date.
 - Otherwise, assign the first day of the month.
- If the month is unknown, then:
 - If the year matches the year of the first dose of investigational product date in this study, then impute the month and day of the first dose date in this study.
 - Otherwise, assign ‘January’
- If the year is unknown, then the date will not be imputed and will be assigned a missing value.

If the imputed date is earlier than birth date, then birth date will be used. If the imputed start date is later than the end date, then the start date will be set as the same date as the end date.

Missing Stop Dates (for AEs not ongoing)

- If the day is unknown, then assign the last day of the month.
- If the month is unknown, then assign ‘December.’
- If the year is unknown, then the date will not be imputed and will be assigned a missing value, and the event will be considered ongoing. If the AE has been recorded as resolved/recovered, all efforts should be made to obtain the date from the Investigator.

If the resulting end date is after the date of study completion / discontinuation/ data cutoff, set the imputed end date as close to the date of study completion / discontinuation/ data cutoff as possible without overwritten existing information

If the year is missing for the start date, and stop date (observed or imputed) is on or after the first dose or event is ongoing. The start date will be imputed as the first dose date.

10.1.4 **Missing Causal Relationship to Investigational Product for Adverse Events**

If the causal relationship to the investigational product is missing for an AE that started on or after the date of the first dose of double-blind investigational product, a causality of “related” will be assigned. The imputed values for causal relationship to investigational product will be used for the incidence summary; the values will be shown as missing in the data listings.

10.1.5 [REDACTED]

[REDACTED]

[REDACTED]

Table 3

The figure consists of a 10x2 grid of horizontal bar charts. The left column, labeled 'H', contains 10 rows of bars. The heights of these bars are as follows: Row 1: ~85%, Row 2: ~95%, Row 3: ~90%, Row 4: ~95%, Row 5: ~90%, Row 6: ~95%, Row 7: ~90%, Row 8: ~95%, Row 9: ~90%, Row 10: ~95%. The right column, labeled 'I', contains 10 rows of bars. The heights of these bars are as follows: Row 1: ~5%, Row 2: ~10%, Row 3: ~5%, Row 4: ~10%, Row 5: ~5%, Row 6: ~10%, Row 7: ~5%, Row 8: ~10%, Row 9: ~5%, Row 10: ~10%. All bars are black on a white background.

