3.3 Blinding and Randomization Methods

In the SAD Period of the study, all subjects receive open-label UX053. In the RD Period of the study, subjects are randomized 3:1 to UX053 and Placebo, using an interactive response technology (IRT) system. The RD Period of the study is double-blind. Each subject will be assigned a unique identification number.

Blind conditions will be established so that Ultragenyx, the subject, and site personnel will not know the identity of a subject's treatment during the RD Period of the study. The only unblinded Ultragenyx members, who will be involved, as needed, in the preparation of the unblinded DMC outputs, are the Independent Statistician, Independent Statistical Programmer and Independent PK Analyst.

Randomization using an IRT system will ensure subjects in the RD Period of the study are blind to treatment. Due to the difference in opacities of the UX053 and the placebo, an unblinded pharmacist will prepare the study drug and an unblinded nurse will prepare the infusion before masking the infusion syringe and tubing with colored covers. Prespecified employees from Ultragenyx who do not have any contact with the investigative sites may also be unblinded as specified in the Blinding Plan.

All imaging assessments will be sent to central readers for evaluation. Readers will be blinded to the subject's treatment.

Treatment assignment for an individual subject should be unblinded by the Investigator only in an emergency, and only if when knowledge of the treatment assignment is urgently needed for the clinical management or welfare of the subject. Unblinding at the study site for any other reason will be considered a protocol deviation.

The Investigator is strongly encouraged to contact Ultragenyx before unblinding any subject's treatment assignment, but priority should be given to the safety of the subject.

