6 ANALYSIS POPULATIONS

6.1 Safety Analysis Set

Safety analysis set will include all enrolled subjects who received any volume of UX053. The primary analysis will be performed on the Safety Analysis Set.

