7.7 Analysis of Primary Endpoints

The primary analysis endpoint is the incidence and severity of TEAEs, serious TEAEs, and related TEAEs in the SAD and RD Periods. The primary analyses will be based on Safety Analysis Set and displayed by analysis group in each period.

Adverse events will be coded by system organ class and preferred term using the Medical Dictionary for Regulatory Activities (MedDRA version 23.1 or above).

An AE (classified by preferred term) will be considered a treatment emergent adverse event (TEAE) if it occurred on or after the first dose of investigational product and was not present prior to the first dose, or it was present at the first dose but increased in severity or frequency. TEAE will be separately reported in SAD and RD Period.

Subject incidence of TEAEs and percentages will be tabulated as the following:

- TEAEs by analysis group in each period, SOC and PT (preferred term) (sorted by descending frequency in the pooled UX053 group by SOC and PT)
- Related TEAEs by analysis group in each period, SOC and PT (sorted by descending frequency by SOC and PT)
- Serious TEAEs by analysis group in each period, SOC and PT (sorted by descending frequency by SOC and PT)
- Serious Related TEAEs by analysis group in each period, SOC and PT (sorted by descending frequency by SOC and PT).
- TEAE by greatest severity, SOC and PT
- Deaths by analysis group in each period, SOC and PT (sorted by descending frequency by SOC and PT).
- TEAEs leading to discontinuation of study by analysis group in each period, SOC and PT (sorted by descending frequency by SOC and PT).

Detailed listings for all AEs, serious TEAEs, AEs leading to the discontinuation of study, AEs leading to the discontinuation of treatment, and death will also be generated.

The severity of all AEs will be based on Common Terminology Criteria for Adverse Events (CTCAE), Version 5.0, published on November 27, 2017, unless the AE is Cytokine Release Syndrome (CRS), in which case the AE will be graded by the American Society for Transplantation and Cellular Therapy (ASTCT) Consensus Grading for CRS ([Lee et al. 2019](#)). If an AE cannot be graded based on CTCAE, the investigator will assign a severity based on 1 = mild, 2 = moderate, 3 = severe, 4 = life threatening, and 5 = Death.

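### The missing-causality rule in SAP 10.1.4 is tied to the first dose of double-blind product, so read literally it covers none of the 8 open-label SAD subjects who will be analysed

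*SAP*

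**What the plan says.** SAP 10.1.4 gives a conservative default for adverse events that lack an investigator causality assessment: they count as *related*. The default applies when the assessment is "missing for an AE that started on or after the date of the first dose of double-blind investigational product". The section adds that the imputed value enters the incidence summary, while listings show causality as missing.

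SAP 3.3 describes the two parts of the study. Of the first it says "In the SAD Period of the study, all subjects receive open-label UX053", and of the second "The RD Period of the study is double-blind".

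SAP 8 records that "the study terminated after enrollment of 4 subjects in Cohort 1S and 4 subjects in Cohort 2S", and that as a result "only analyses specific to SAD cohorts 1S and 2S will be provided".

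SAP 7.7 treats an adverse event as treatment-emergent "if it occurred on or after the first dose of investigational product and was not present prior to the first dose", or if it was already present at first dose and then worsened. SAP 10.1.3, on partial AE and medication dates, uses the same unqualified reference point, for example "If the year matches the year of the first dose of investigational product date in this study". SAP 4.1 and 7.7 include related TEAEs in the primary endpoint, and 7.7 plans tables of related and serious related TEAEs.

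**The concern.** The word double-blind limits the imputation rule to subjects who received blinded product. No subject in the analyses that will be produced did so. The word looks like a carry-over from the RD design.

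The rule is operative, because it decides how an event is counted in a component of the primary endpoint. A programmer who followed the text exactly would have no instruction for a SAD event with causality missing at database lock. The readable SAP has no other rule for missing causality, and SAP 1 gives the SAP precedence over the protocol on data analysis. Such an event could be left out of the related-TEAE tables, the opposite of the conservative treatment the rule was written to provide. With cohorts of 4, one subject's classification is visible in the result.

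**Working it through.** This is a check of wording and a count. The plan states no figure for it that could be reproduced.

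**Step 1: who received double-blind product.** In the readable SAP, apart from 10.1.4, the term appears in the design text of Section 3, in the Figure 1 labels and in Section 3.3. Each time it describes the RD Period.

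- Enrolled (SAP 8): 4 in 1S + 4 in 2S = 8.
- Enrolled in double-blind cohorts: 0.
- Covered by 10.1.4 as written: 0 of 8.
- Covered if the word is removed: 8 of 8.

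All 8 enter the Safety Analysis Set only if all were dosed, because SAP 6.1 states "Safety analysis set will include all enrolled subjects who received any volume of UX053".

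**Step 2: what the other first-dose rules use.**

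| SAP section | Rule anchored on first dose | Double-blind qualifier? |
|---|---|---|
| 5.1 | Baseline | No |
| 5.2 | Duration of exposure | No |
| 5.3 | Study day and analysis periods | No |
| 7.1 | Periods shown on graphs | No |
| 7.6 | Prior and concomitant medication | No |
| 7.7 | TEAE definition | No |
| 10.1.3 | Partial AE and medication dates | No |
| 10.1.7 | Mapping of unscheduled visits | No |
| 10.1.4 | Missing causality | **Yes** |

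That is 8 sections without the qualifier and 1 with it. The count is of readable sections only, since parts of the SAP are redacted. Section 3.2 also mentions a first dose, but there it describes spacing between subjects, so it is not counted.

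**Step 3: did early termination create the mismatch?** SAP 3.5 planned at least 10 SAD and 16 RD subjects, 26 in all. Under that plan the wording would already have excluded the 10 open-label subjects: 10/26 = 38%. Stopping early raised the excluded share to all of those enrolled.

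**Step 4: possible effect on the related-TEAE incidence.** Suppose one subject has a TEAE with causality still missing at lock and no other related TEAE. Whether the rule applies moves that subject in or out of the numerator, a shift of 1/n:

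- one cohort, n = 4: 1/4 = 25 percentage points;
- total, n = 8: 1/8 = 12.5 percentage points.

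These are conditional figures and do not estimate what happened. The documents do not say how many AEs had missing causality, and the number may be zero. If it is zero, the shift is zero.

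**The case against.** The strongest reply is that the rule will probably never be used. Protocol Appendix 1 has AEs without a causality assessment followed up until one is assigned. Appendix 2 requires relationship to study drug among the details of every AE, and Appendix 5 has missing data resolved with the investigator. SAP 10.1 adds a review of missing data before lock. Eight subjects are a small set to query. This stands, and it is why the practical effect is put at probably nil. It does not make the wording right: the SAP includes a fallback despite these controls, and the fallback should apply to the subjects being reported.

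A second point is that the rule acts on events, so 0 of 8 subjects does not measure impact. That is fair. The figure describes the reach of the rule; the number of affected events is unknown.

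Third, most of the eight sections govern other derivations, so a different anchor there does not strictly contradict 10.1.4. That also stands in part. The direct mismatch is with 7.7, which defines the events to be classified, and 10.1.3 is adjacent. The other six show only that the qualifier is out of line with the SAP's usual usage.

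Finally, the intended meaning is clear from the heading of 10.1.4 and from 7.7, and much other RD text remains in the SAP. The intent is almost certainly first dose of any study product. But most of the leftover RD text is simply unused, whereas this word restricts a rule that has to work on the SAD data.

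An affected event would in any case still appear in the overall TEAE table and, with causality shown as missing, in the listings.

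**Conclusion.** The concern holds as a minor inconsistency. As written, SAP 10.1.4 reaches 0 of the 8 enrolled subjects and disagrees with the TEAE definition in SAP 7.7. Its effect on the related-TEAE incidence would be 25 points per affected subject in a cohort, or 12.5 points overall. That requires causality unresolved at lock and no other related TEAE in that subject, and it assumes all 8 subjects were dosed. There is no evidence that any such event exists, and the expected practical effect is nil. No analysis set or endpoint definition is in question.

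**What to change.** Delete the word double-blind from SAP 10.1.4, so that the rule runs from the first dose of investigational product, in line with 7.7 and 10.1.3. Coverage then becomes 8 of 8 enrolled subjects. If the SAP is already final, one sentence in the clinical study report does the same job, since SAP 1 provides for changes to be documented there.

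Optionally, add a footnote to the related-TEAE tables giving the number of imputed causalities, including when it is zero.

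The cost is one word in the SAP, plus a footnote if wanted. No new data or analysis is needed.

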10.1.6 Missing Data for Other Efficacy Endpoints

When a change from baseline is assessed, missing data will not be imputed and only subjects with a baseline and at least 1 post-baseline measurement will be included in the analysis.

For the weekly nutrition diary data, at least 3 complete days out of 7 will be necessary for the calculation of mean weekly intakes. For each week, if more than 4 days are either missing or not checked as complete, the nutrition diary data is considered missing for that week.

10.1.7 Visit Time Windows

For an unscheduled visit that occurred after the first dose date of IP, the unscheduled visit will be mapped into the closest post-baseline study scheduled visit for the assessment based on the study day of the unscheduled visit, and the target study day of the scheduled visit of the assessment in the protocol. If the unscheduled visit has equal distance to the 2 study scheduled visits, it will be mapped to the later visit.

The unscheduled visit will be only mapped to study visit within each period during it occurs.

When there is more than 1 measurement mapped to the same scheduled visit (including the original measurement taken from the scheduled visit), the measurement taken on the scheduled visit will be used if it is not missing, otherwise the visit closest to the target day will be used. If more than 1 visit has equal distance to the target day, then the later visit will be used. If more than 1 measurement is collected on the same day, the time or sequence

number will be used to select the latest record. For listings and shift tables, all data points will be included.

Early termination visit will follow the same rule for unscheduled visit as described above.

Plasma fibrinogen & d-dimer			X ^g	X			X				
Hematology	X	X ^d	X	X	X	X	X	X	X	X	
Chemistry ^h	X	X ^d	X	X	X	X	X	X	X	X	
Urinalysis ⁱ	X	X ^d	X	X	X	X	X	X	X	X	
Serum CRP			X ^d	X	X	X	X	X	X	X	
Liver											
Liver MRI		X									
Liver MRS ^j		X									
FibroScan or ultrasound elastography	X										
PT/INR ^g	X	X ^d	X		X					X	
Serum HDL & LDL ^k	X	X ^d									
Cardiac											
Serum CK-M/B	X	X ^d									

Day (D) / Week (W)	Screening ^a	Treatment Period								EOS I (D90)/ ET ^b	
		BL	Single Ascending Dose Period								
		D0	D1	D4	D7	D14	D21	D28	D42		
Visit Window Relative to Baseline	-	-	-	± 1 day		± 2 days					
Plasma BNP	X	X ^d									
Serum troponin I	X	X ^d									
ECG	X	X ^d	X							X	
Skeletal Muscle & Strength											
Serum CK	X	X ^c									
Serum myoglobin	X	X ^d									
Calf MRS ^j	X										
HHD	X	X ^d									
Clinician- & Patient-reported Outcomes											
PROMIS questionnaires & SF-36v2		X ^d									
GNEM-FAS expanded version		X ^d									
Nutrition diary	X ^l	X ^l	X ^l	X ^l	X ^l	X ^l	X ^l	X ^l	X ^l	X ^l	
Exploratory Assessments											
Serum ketones	X	X ^d	X	X	X	X	X	X	X	X	
Urine beta hydroxybutyrate ⁱ	X	X ^d	X	X	X	X	X	X	X	X	
Serum biotinidase	X	X ^d									

Day (D) / Week (W)	Screening ^a	Treatment Period								EOS I (D90)/ ET ^b	
		BL	Single Ascending Dose Period								
			D0	D1	D4	D7	D14	D21	D28		
Visit Window Relative to Baseline	-	-	-	± 1 day		± 2 days					
CGM ^m	X ^m	X ^m	X ^m	X ^m	X ^m	X ^m	X ^m	X ^m	X ^m	X	
Plasma Glc ⁴	X	X ^d									
Urine Glc ⁱ	X	X ^d			X					X	
Whole blood RNA expression	X										
AGL variant analysis	X										
Blood Cell Pellet for Future Use	X	X ^d									
Serum & Plasma for Future Use ⁿ		X ^d			X			X		X	

Footnotes continue on the following page.

^a Screening assessments can be done over the course of multiple days. There must be 10 to 14 days between any assessments that are measured at both the Screening Visit and the BL Visit.

^b In the event a subject has an ET, all efforts will be made to monitor the subject through the end of the study. At minimum, a safety follow-up phone call will occur within the 4 weeks following the subject's last treatment.

^c Complete physical exam is required at the Screening, BL, and EOS I/ET Visits. Targeted physical exams may be performed at the D1 Visit.

^d Assessments to be performed prior to dosing. The following assessments can be collected within a week prior to dosing, as long as there is 10 to 14 days between assessments that are repeated at the Screening Visit and the Baseline Visit: HHD, PROMIS questionnaires, SF-36v2, and GNEM-FAS expanded version.

^e Refer to Table 6 for the timing of vital sign assessments during dosing.

^f Refer to Table 7 for details of PK sampling. Please note that sample collections are marked for D1, D4, D7, D14, D21, and D28 in this table (Table 4) corresponding to a sample collection 1, 4, 7, 14, 21, and 28 days after infusion of UX053 on D0 as outlined in the final rows of the first column in Table 7.

^g Sample to be collected pre-dose and at the end of the infusion. Post-infusion blood samples should be collected in the opposite arm of the infusion to avoid dilution.

^h Close monitoring is required for subjects who develop elevations in ALT > 3x ULN and > 2x their baseline value, or elevation in ALT > 3x ULN with INR > 1.5. This includes repeating liver enzymes and INR within 48 hours and consideration of additional diagnostic tests such as liver ultrasound (Section 10.1.5).

ⁱ All efforts should be made for urine collections to be consistently taken from the first morning void.

^j Liver and calf MRS are only required at sites with capability. Scanning for liver and calf MRS can be conducted immediately following the liver MRI.

^k A 3 to 4 hour fasting period is preferred, but not required, prior to blood collection for serum HDL and LDL. All efforts should be made to obtain samples for HDL and LDL consistently for a given subject.

^l The nutrition diary recordings should be recorded daily from the Screening Visit through the EOS I D90/ET Visit.

^m The subject will receive CGM and HHG devices and will be trained on proper use at the Screening Visit. The CGM device will be worn continuously from the Screening Visit to the EOS I D90/ET Visit. If the CGM device alarm notifies a subject that their blood sugar is abnormally high or low or the subject suspects their blood sugar is abnormally high or low, the subject will need to check their blood sugar with a HHG device that will be provided by Ultragenyx at the Screening Visit (ISV for RD). When CGM data is being collected, all subjects will connect their CGM and HHG devices to a study-provided laptop weekly and upload CGM and HHG data. At remote visits, in conjunction with assessments performed by a home health nurse, the site will contact subjects by telephone or videoconference to confirm the CGM device is properly in use and data was uploaded; answer any questions regarding or help troubleshoot (if necessary) CGM device use; and review CGM data, HHG data (when applicable), and nutrition diary entries; these telephone calls will occur as needed for the SAD Period between Day 28 and Day 90/EOS I Visits. At in-clinic visits, a conversation between the site and the subject should occur to ensure CGM compliance and troubleshoot if needed.

ⁿ Serum and plasma samples will be collected for future biomarker assessments yet to be determined.

Note: White columns indicate in-clinic visits (Screening, BL D0, D1, and EOS I D90/ET). Gray columns indicate visits conducted at home by a home health nurse in conjunction with a phone call as needed (D4, D7, D14, D21, D28, and D42).

Note: Laboratory assessments included in chemistry, hematology, and urinalysis are provided in Appendix 3.

AGL, amylo- α -1,6-glucosidase 4-alpha-glucanotransferase; AH50, alternative complement activity; BL, baseline; BNP, B-Type Natriuretic Peptide; CGM, continuous glucose monitor; CH50, classical pathway complement activity; CK, creatinine kinase; CK-M/B, CK-muscle/brain; COVID-19, coronavirus disease 2019; CRP, C-reactive protein; D, day; ECG, electrocardiogram; EOS, end of study; ET, early termination; GDE, glycogen debranching enzyme; Glc4, glucose tetrasaccharide; GSD, glycogen storage disease; GNEM-FAS, GNE Myopathy Functional Activities Scale; HHD, handheld dynamometry; HHG, handheld glucometer; HDL, high density lipoprotein; IL-6, interleukin-6; LDL, low density lipoprotein; MRI, magnetic resonance imaging; MRS, magnetic resonance spectroscopy; PROMIS, Patient-Reported Outcomes Measurement Information System; PBMC, peripheral blood mononuclear cell; PK, pharmacokinetic; PT/INR, prothrombin time/international normalized ratio; sC5b-9, soluble Complement 5b-9; SF-36v2, Short Form Health Survey 36 Version 2.

Table 6: Schedule of Vital Sign Assessments

Study Period	SAD Period	RD Period				
Time	Day 0	Week 0	Week 2	Week 4	Week 6	Week 8
Pre-Infusion						
Within 30 min of initiating the infusion	X	X	X	X	X	X
During infusion (4 hr infusion)						
15 min (\pm 5 min)	X	X	X	X	X	X
30 min (\pm 5 min)	X	X	X	X	X	X
45 min (\pm 5 min)	X	X	X	X	X	X
1 hr (\pm 10 min)	X	X	X	X	X	X
2 hr (\pm 10 min)	X	X	X	X	X	X
3 hr (\pm 10 min)	X	X	X	X	X	X
4 hr (\pm 10 min)	X	X	X	X	X	X
Post-infusion (24 hr monitoring)^a						
5 hr (\pm 5 min)	X	X	X	X	X	X
6 hr (\pm 5 min)	X	X	X	X	X	X
7 hr (\pm 10 min)	X	X	X	X	X	X
8 hr (\pm 10 min)	X	X	X	X	X	X
9 hr (\pm 10 min)	X	X	X	X	X	X
10 hr (\pm 10 min)	X	X	X	X	X	X
16 hr (+/- 1hr)	X	X	X	X	X	X
24 hr (+/- 2hr)	X	X	X	X	X	X

hr, hour; min, minute; RD, Repeat Dose; SAD, Single Ascending Dose.

^a All post-infusion time points refer to time from the beginning of the infusion.

Table 7: Schedule of PK Assessments during and following Treatment Infusion

Study Period	SAD Period		RD Period			
Sample Type	Blood	Plasma	Blood	Plasma	Blood	Plasma
Analyte	AGL mRNA	ATX95	AGL mRNA	ATX95	AGL mRNA	ATX95
Infusion	Day 0 Infusion		Week 0 Infusion		Week 8 Infusion	
Pre-infusion						
Within 1 hr prior to initiating infusion	X	X	X	X	X	X

During infusion (4 hr infusion)						
1 hr (± 10 min) ^a	X	X	X	X	X	X
3 hr (± 10 min)	X	X	X	X	X	X
Post-infusion						
4 hr (± 10 min) ^b	X	X	X	X	X	X
4.5 hr (± 10 min)	X	X	X	X	X	X
5 hr (± 10 min)	X	X	X	X	X	X
6 hr (± 20 min)	X	X	X	X	X	X
8 hr (± 30 min)	X	X	X	X	X	X
10 hr (± 30 min)	X	X	X	X	X	X
24 hr (± 2 hr); Day 1	X	X	X	X	X	X
96 hr (± 24 hr); Day 4	X	X				
168 hr (± 24 hr); Day 7	X	X	X	X	X	X
336 hr (± 24 hr); Day 14	X	X	X ^c	X ^c	X	X
504 hr (± 24 hr); Day 21	X	X				
672 hr (± 24 hr); Day 28	X	X			X	X

